7.2. Setting

The target population of this study is adult patients with RCC and medical records available at HDSF data lake. Estimated number of patients in this study is 220-550. The inclusion criteria is a diagnosis of renal cell carcinoma (ICD-10: C64) between January 2010 and December 2021 (Figure 1). Advanced/metastatic disease stage (mRCC) will be assessed based on ICD-10 diagnosis code for metastasis (C77*-C79*), American Joint Committee on Cancer (AJCC) stage 4, visit to oncologist (specialty code 65), or initiation of treatment for mRCC.

[figure not shown]

Figure 1. Graphical illustration of study time windows and corresponding analyses.

The data collected has been generated as part of standard clinical care, treatment, and follow-up of patients with RCC. In accordance with the Finnish Act on Secondary Use of Health and Social Data 552/2019 (in Finnish: Laki sosiaali- ja terveystietojen toissijaisesta käytöstä), health registry data can be processed in scientific studies without patient consent. The purpose of this act is to establish conditions for the effective and secure processing of, and access to, personal health and social data for certain secondary purposes, such as research and statistics, innovation and development, knowledge management, teaching and authority planning. Thus, the Secondary Act creates a clear legal basis for the use of such registered data for research and innovation related to, for example, the health and well-being of citizens, the prevention of

disease and the development of new treatment methods. This relatively new legislation is also a welcome unification of the fragmented Finnish national rules regarding the use of healthcare and social welfare data. In addition, it takes into consideration current data protection requirements.

In the primary objective 1 (characteristics), all RCC patients will be analysed (local and metastatic diseases separately), while in the other objectives only treated mRCC patients will be analysed. Therefore, there are two cohorts to be analysed: 1) characteristics cohort (including all RCC patients), 2) mRCC cohort (including only treated mRCC patients).

Definitions for mRCC cohort

Index: Date of the first mRCC diagnosis; date of the metastatic disease identified as first of the following after the initial RCC diagnosis

- ICD-10 diagnosis code (C77*-C79*) for metastatic disease
- AJCC stage 4
- Visit to oncologist (specialty code 65) with RCC as main diagnosis

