- Treatment initiation for mRCC (sunitinib, pazopanib, cabozantinib, ipilimumab, nivolumab)

When analyzing the treatment outcomes, index is defined as the date of the treatment initiation.

End of follow-up (whichever of the following occurs first):

- Death
- Moving outside of HDSF
 - Approximated using data of healthcare contacts; no contacts to specialty care of HDSF within 2 years (patient censored at the last recorded visit)
- End of study (31.12.2021)

Length of follow-up (in years): ('end of follow-up' – 'index' + 1)/365.25

Definitions for characteristics cohort

Index:

- For mRCC patients, same as for the mRCC cohort (i.e. approximated metastasis date)
- For RCC patients, the date of the first record of RCC diagnosis (ICD-10: C64)

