7.2.2. Exclusion criteria

For the **characteristics cohort**, patients meeting any of the following criteria will be excluded from the study:

- Prevalent mRCC patients (i.e. diagnosis of metastatic RCC before 1.1.2010)
- Prevalent RCC patients (i.e. diagnosis of RCC before 1.1.2010) if there is no records of metastatic disease during 2010-2021

For the **mRCC cohort**, patients meeting any of the following criteria will be excluded from the study:

- Prevalent patients with mRCC (i.e. diagnosis of metastatic RCC before 1.1.2010)
 - Note that patients with local RCC before 2010 are included in this study if the disease has metastasised during 2010-2021
- Patients without treatment for mRCC (see Table 3 for details)

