7.7.3. Treatment outcomes

Primary objective 3:

The treatment outcomes will be assessed using time-to-event analysis, namely Kaplan-Meier fit or other relevant competing risk models. For each outcome, the time will be defined as follows (Figure 3):

- overall survival:
 - time from index until death (event) or end of study (censoring event)
 - when analysing by treatment lines, start the time from initiation of each treatment line
- progression free survival (PFS, defined using time to next treatment (TTNT) proxy):
 - time from initiation of the current treatment line until the initiation of the next treatment line (event), death (competing risk/event), or end of study (censoring event)

The Kaplan-Meier fits will be visualized, and the median survival/PFS of the patients will be reported as well, if reached.

Additionally, corresponding Cox proportional-hazards model will be fitted, including clinical variables as covariates (including but not limited to age, sex, IMDC risk score, diagnosis year, and treatment line number). The hazard ratios, 95% confidence intervals and p-values corresponding to each covariate will be reported.

[figure not shown]

Figure 3. Graphical illustration of definitions of treatment outcomes. Abbreviations: LOT = line of treatment.

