7.7.6. Changes in coding practices over time

Exploratory objective 1:

Assess changes in coding practices as a proportion of patients with data available respect to the diagnosis year of advanced/metastatic RCC. Variables of interest include but are not limited to

- structured IMDC risk score
- ICD-10 diagnosis for metastatic disease (C77*-C79*)

Other aspects of changes in coding practices may also be analyzed, if reasonable.

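### In Cox models for line 2 and later, and more weakly in models pooled over lines, the diagnosis-year hazard ratio is biased towards apparent worsening when prognosis varies beyond the covariates

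*Combined protocol and SAP*

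**What the plan says.** Section 7.7.3 of the combined protocol and SAP plans Cox models with clinical covariates, "including but not limited to age, sex, IMDC risk score, diagnosis year, and treatment line number", each reported with a hazard ratio, 95% confidence interval and p-value. It does not say which diagnosis the year refers to.

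For survival by line, the same section says: "when analysing by treatment lines, start the time from initiation of each treatment line". Time to next treatment also starts at the current line. Section 7.2.3 applies stratification by line to primary objective 3. Section 7.2 closes follow-up at "End of study (31.12.2021" or earlier.

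Two places bear on the meaning of the year. Section 7.7.6, the only other use of the term, speaks of the "proportion of patients with data available respect to the diagnosis year of advanced/metastatic RCC". Section 7.2 defines the mRCC cohort's index as the first mRCC diagnosis and adds: "When analyzing the treatment outcomes, index is defined as the date of the treatment initiation".

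On entry, 7.2.1 asks for a C64 diagnosis in 2010-2021, while a note in 7.2.2 says that "patients with local RCC before 2010 are included in this study if the disease has metastasised during 2010-2021".

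No section discusses how the closing date selects patients into later lines, or adjusts for the time taken to reach a line.

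**The concern.** A patient with mRCC diagnosed at the start of 2010 has 12 years in which to reach line 2 or 3. One diagnosed at the start of 2019 has 3 years. Among recent diagnoses, later lines therefore hold mainly patients whose earlier lines ended fast, and those patients tend to do worse afterwards. This is selection into the analysis set. It is not right-censoring within that set, so the partial likelihood does not remove it. Age, sex and first-line IMDC category capture only part of a patient's speed through earlier lines.

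The cover page says outcomes will be looked at over time, and 7.7.3 offers no other calendar-time analysis of outcomes. The year HR is likely to be read as that result. A bias above 1 would look like worsening survival in a period that section 5 describes as bringing several new treatments.

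**Working it through.** **Plan's own figure.** Section 7.5 gives 1,100 RCC patients, 20-50% becoming metastatic: 1,100 x 0.20 = 220 and 1,100 x 0.50 = 550. This agrees with the stated 220-550. It includes untreated patients, so the treated cohort is smaller. The plan states no power or hazard-ratio figure.

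**Step 1: the mechanism by hand (assumed inputs).** Let line durations be exponential with median 0.9 years, so the rate is ln 2 / 0.9 = 0.770 per year. Let half the patients have rate multiplier z = 0.5 and half z = 1.5 (mean 1, variance 0.25), with z also multiplying the hazard of death. The chance of moving on after a line is the same for both types, so it cancels. With t years from mRCC diagnosis to the end of data and x = 0.770 z t:

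- P(line 2 can start) is proportional to 1 - exp(-x)
- P(line 3 can start) is proportional to 1 - exp(-x)(1 + x)

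| Line | t (years) | z = 0.5 | z = 1.5 | Share with z = 1.5 | Mean z at entry |
|---|---|---|---|---|---|
| 2 | 12 | 0.990 | 1.000 | 0.502 | 1.002 |
| 2 | 3 | 0.685 | 0.969 | 0.586 | 1.086 |
| 3 | 12 | 0.945 | 1.000 | 0.514 | 1.014 |
| 3 | 3 | 0.321 | 0.860 | 0.728 | 1.228 |

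The hazard at line start for a diagnosis 9 years later is 1.086/1.002 = 1.08 times as high in line 2 and 1.228/1.014 = 1.21 times in line 3. Line 1 has no such selection. If every z = 1, all ratios are 1.

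**Step 2: simulated Cox models.** mRCC uniform over 2010-2021, no calendar trend, same median, 65% moving on, frailty variance 0.25-1.0 (gamma or log-normal). HR for mRCC diagnosed 9 years later, range over runs:

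| Model | Frailty present | Half the frailty captured by a covariate |
|---|---|---|
| Line 1 | 0.99-1.04 | not run |
| Line 2 | 1.05-1.42 | 1.03-1.13 |
| Line 3 | 1.09-1.78 | 1.12-1.28 |
| Pooled | 1.02-1.18 | 1.00-1.07 |

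With no frailty the HRs are about 1 (at most 1.07). With 220-550 patients and unadjusted frailty, a nominal 5% test rejected in 9-19% of samples for line 2, 11-26% for line 3 and 3-7% for line 1. Adding log time from mRCC diagnosis to line start brought the later-line HRs to 0.96-1.18.

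**Step 3: if the year is that of initial RCC diagnosis.** Assumptions: RCC diagnosed uniformly from 1995; 55% synchronous metastasis, otherwise a mean interval of 4 years; HR 1.5 for the under-1-year factor and 1.4 for each other IMDC factor; median OS 3 years; adjustment for IMDC category; no calendar trend. The mean diagnosis-to-treatment interval among included patients falls from 7.9 years (2005) to 1.4 (2012) and 0.16 (2021).

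| Extra HR per year of interval | 10-year HR, RCC year | Same, RCC only from 2010 | 10-year HR, mRCC year | Same, RCC only from 2010 |
|---|---|---|---|---|
| 1.00 | 1.07 | 1.02 | 1.01 | 0.96 |
| 0.97 | 1.23 | 1.05 | 1.01 | 0.93 |
| 0.93 | 1.47 | 1.11 | 1.00 | 0.89 |

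For RCC year with diagnoses from 1995, a false finding of worsening occurred in 3%, 18% and 50% of samples at n = 220, and in 9%, 43% and 91% at n = 550.

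**The case against.** **The natural reading is mRCC year, and there line 1 is sound.** This stands. Sections 7.2 and 7.7.6 both point to mRCC diagnosis, and the first-line HR is then about 1.0. A reader might infer that the reported year HR will show worsening survival in general, or that the plan intends initial RCC year. The documents support neither. The RCC-year arm is an ambiguity, and its size depends on how prognostic the interval is and on which entry rule governs.

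**Listing line number as a covariate implies a pooled model, where the bias is small.** This largely stands: 1.0 to 1.2 pooled. But 7.7 and 7.2.3 also call for outcomes by line, so line-specific models are plausible and are not ruled out.

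**The sizes rest on figures outside the documents, and IMDC would absorb some heterogeneity.** Also true. Capturing half the frailty cuts line 2 to 1.03-1.13. Line 3 stays at 1.12-1.28, so the bias shrinks without vanishing.

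**The plan is mainly descriptive, no objective asks whether newer treatment helped, and the covariate list is open-ended.** This lowers the stakes. An open list permits the adjustment but does not commit to it, while reporting of the year HR is committed.

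**Calendar year of first-line start is not a neutral substitute.** Correct. With 20-40% assumed to defer treatment and to have better prognosis (HR 0.6), first-line-start year gave a 9-year HR of 0.97-0.91, a spurious improvement, against 1.07-1.04 for mRCC year.

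**Conclusion.** The concern holds for models of line 2 and later, and weakly for models pooled over lines. There the diagnosis-year HR is biased above 1 whenever patients differ in prognosis beyond the covariates. The direction follows from the plan's own rules: time restarts at each line and data end on 31.12.2021. The sizes do not. They rest on the assumed line duration, progression share and frailty: roughly 1.05-1.4 in line 2, 1.1-1.8 in line 3 and 1.0-1.2 pooled over 9 years, and close to 1 without unmeasured heterogeneity.

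The first-line model with mRCC year is essentially unbiased, with two reservations. Deferred treatment can push its HR slightly up. If only RCC first diagnosed from 2010 enters, the simulated 10-year HR is 0.89-0.96, the opposite direction. With initial RCC year, first line can be biased upward by anything from almost nothing to a large amount. Sections 7.2.1 and 7.2.2 must be reconciled before that can be judged. This is a worthwhile, inexpensive improvement; it does not undermine primary objective 3.

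**What to change.** In 7.7.3:

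1. Define the covariate as calendar year of mRCC diagnosis, matching 7.7.6.
2. Draw any conclusion about calendar time from the first-line model only.
3. In models for line 2 and later, or pooled over lines, add log time from mRCC diagnosis to the start of the current line, and state that the year HR there is not a time trend.
4. Offer year of first-line start as a sensitivity analysis, noting that deferred treatment can bias it the other way. Line-start year should not replace diagnosis year in later-line models: with prevalent mRCC excluded, it gave 0.64-0.85 over 9 years with no true trend.

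In 7.2.1 and 7.2.2, reconcile whether RCC first diagnosed before 2010 enters the mRCC cohort. If initial RCC year is kept in any model, add the continuous diagnosis-to-treatment interval, already listed in 7.7.1. In the scenarios with RCC from 1995 this brought the 10-year HR to 1.01-1.02.

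The cost is one extra covariate computed from dates already collected and a few sentences of text. Some residual bias remains (0.96-1.18 in later lines after adjustment), and the study gives up a headline calendar trend for later lines.

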7.7.4. Morbidity

Secondary objective 1:

Morbidity will be assessed using data of co-diagnoses, procedures, and medications before and after diagnosis of advanced/metastatic RCC using all available data (ICD-10, procedure codes, and ATC-codes) in baseline and during the follow-up, respectively. The number (N) and proportion (%) of patients with each morbidity will be reported.

The list of morbidities of interest are:

- co-diagnoses using ICD-10 codes
 - especially interest of infections (ICD-10: A00*-B99*) and hypertension (ICD-10: I10)
- procedures related to kidneys
 - all KA* (kidneys and pelvis of kidneys) and KA_* (diagnostic radiology of kidney and pelvis of kidneys) procedures codes
- use of antibiotics (ATC-code: J01*, J02* and J04*) and antihypertensive medication (ATC-code: C02*)

If data coverage seems low, use of antibiotics and antihypertensives can be used as a proxy for infections and hypertension, respectively, along with the diagnosis (ICD-10) data.

Therefore, diagnoses and medications will be analyzed as a combination instead of separately.

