6.2. Secondary objectives

1. Assess morbidity of metastatic RCC including
 - a. co-diagnoses and procedures
 - b. infections and antibiotic use
 - c. antihypertensive use before and after mRCC diagnosis, as applicable

2. Assess speciality care healthcare resource use (absolute, per patient, per patient year)
 - a. cumulatively over time from diagnosis
 - b. by treatment line

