7.3. Variables

Source for all variables is the data lake of HDSF.

Table 2. List of study variables. Abbreviations: PO=primary objective, SO=secondary objective.

Variable	Role/Relevant objective	Operational definition
ICD-10 diagnoses; RCC diagnoses	Patient inclusion/exclusion IMDC risk category	yes/no
ICD-10 diagnoses: co-diagnoses (e.g. renal insufficiency and hypertension)	PO1, SO1	yes/no; co-diagnoses before and after index
Date of birth	Patient inclusion PO1	Date; age defined at index based on birth date
Date of death	End of follow-up PO3	Date
Gender	PO1	Female/male
Home municipality	Patient inclusion End of follow-up	Home municipality at each healthcare contact
Weight	PO1	kg
Height	PO1	m
Body mass index (BMI)	PO1	derived from weight and height
Smoking status (if available in structured format)	PO1	yes/no
Outpatient visits (including emergency room visits)	Patient inclusion and index definition (visits to oncologist) SO2	Date, physician's specialty, type of arrival
Hospitalizations	SO2	Start and end dates
Procedures and operations (including nephrectomy)	PO1 SO1 SO2	Procedure code, date
Medical imaging	SO1 SO2	Imaging code, date
Medications; including - hospital medications - prescriptions	Patient inclusion/exclusion and index definition PO2 PO3 SO1 SO2	Dates, ATC-codes, active substance
Laboratory testing	IMDC risk category PO1	Dates, test id, result
Zubrod/ECOG performance status	IMDC risk category PO1	scale 0-5; converted to Karnofsky
PAD histology (if available in structured format)	PO1	
Staging of RCC, the tumor-node-metastasis (TNM) classification	Patient inclusion and index definition PO1	scale 1-4 (stages)

PFIZER CONFIDENTIAL

Table 3. List of medications for RCC treatment. ATC= Anatomical Therapeutic Chemical.

	Active substance	Brand name	ATC-code at the moment in use	ATC-code previously in use
Oral medications	axitinib	Inlyta	L01EK01	L01XE17
	everolimus	Afinitor	L01EG02	L01XE10
	cabozantinib	Cabometyx	L01EX07	L01XE26
	pazopanib	Votrient	L01EX03	L01XE11
	sorafenib	Nexavar	L01EX02	L01XE05
	sunitinib	Sutent	L01EX01	L01XE04
Intravenous medications	ipilimumab	Yervoy	L01XC11	
	nivolumab	Opdivo	L01XC17	

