7.7.1. Patient characteristics

[figure not shown]
Primary objective 1:

Demographical and clinical variables of RCC and mRCC patients will be summarized at index. Treated and non-treated mRCC patients will be analysed separately. For laboratory measures and performance status, the closest available measure +/- 90 days from index will be utilized. In case of a high rate of missing values, the time window can be extended to 6 months.

The demographical and clinical variables include but are not limited to:

- age at index
- sex
- history of renal insufficiency (any records until index)
 - ICD-10 code: N17-N19
- history of dialysis (any records until index)
 - procedure codes: TK800, TK829, TK810,
 - ICD-10 code: Z49

PFIZER CONFIDENTIAL

- history of kidney transplant (any records until index)
 - procedure codes: KAS10, KAS20
 - ICD-10 code: Z94.0
- history of nephrectomy (any records until index)
 - procedure codes: KAC*, KAD*, KAS40, KAS41
 - ICD-10 code: Z90.5
- performance status at index
 - Karnofsky (converted from Zubrod/ECOG)
- time from initial diagnosis of RCC to initiation of treatment for metastatic RCC
- various laboratory measures (e.g. hemoglobin, serum calcium, neutrophiles, thrombocytes, creatinine, albumin, eGFR)
- smoking status (if available in structured format)
- histology (if available in structured format)
- BMI (if available in structured format)

For categorical variables, the number (N) and the proportion (%) of patients in each class will be reported. For continuous normally distributed variables, mean and standard deviation (SD) will be reported. For continuous, non-normally distributed variables, median, the 1st quartile and the 3rd quartile will be reported.

The difference between strata will be tested using chi-squared/Fisher's exact test (categorical variables), t-test (continuous normally distributed variables) and Kruskal-Wallis test (continuous non-normally distributed variables).

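### The before-and-after percentages for infections and antibiotic use in 7.7.4 are not comparable, because the share with any record depends on window length and the two windows are not matched

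*Combined protocol and SAP*

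**What the plan says.** Section 7.7.4 (Morbidity) compares two periods, "before and after diagnosis of advanced/metastatic RCC using all available data (ICD-10, procedure codes, and ATC-codes) in baseline and during the follow-up, respectively". Its only stated output is this: "The number (N) and proportion (%) of patients with each morbidity will be reported". Table 2 in section 7.3 codes co-diagnoses as "yes/no; co-diagnoses before and after index", which is a flag and not a count.

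The items of interest include infections (ICD-10 A00-B99) and "use of antibiotics (ATC-code: J01*, J02* and J04*) and antihypertensive medication (ATC-code: C02" codes. In section 6.2 the before-and-after wording is attached only to item 1c, "antihypertensive use before and after mRCC diagnosis, as applicable". Section 7.7.4 extends it to diagnoses, procedures and medications in general.

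On window length:
- Section 7.2 sets "End of follow-up (whichever of the following occurs first" and lists death, moving out of the district (approximated by two years without specialty-care contact) and 31.12.2021.
- No baseline length appears in the text of 7.7.4.
- Section 7.7.1 looks back without limit for named history items, for example "history of renal insufficiency (any records until index".
- Section 7.2.2 excludes "Prevalent patients with mRCC (i.e. diagnosis of metastatic RCC before 1.1.2010", which can be applied only with records from before 2010. The date on which data lake records begin is not stated.

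Section 7.7.5 scales resource use per patient-year. Section 7.7.4 does not do so for morbidity, and the limitations in 7.9 do not mention unequal observation time.

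**The concern.** For an event that can recur, the share of patients with at least one record rises with observation time even when the rate is constant. The after period is cut short by death in a disease that section 5 calls often fatal. The before period cannot be cut short in that way, because every patient is alive at index. Two yes/no percentages over such periods mix the event rate with the length of observation.

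What is at stake is the message of secondary objective 1. A reader who sees fewer patients with infections or antibiotic use after mRCC than before may conclude that the burden fell, when the rate was unchanged or had risen.

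**Working it through.** **Plan's own figure.** Section 7.5 gives an mRCC cohort of 220-550. This reproduces: 1,100 x 0.20 = 220 and 1,100 x 0.50 = 550. It does not enter the percentages below, and 7.7.4 states no figure of its own.

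**Inputs from the documents.** Index dates run from 1.1.2010 to 31.12.2021, a span of 12 years (7.2.1). Follow-up ends at death or 31.12.2021 at the latest (7.2).

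**Assumptions, because the documents give no value.** Event rate λ of 0.1, 0.2 or 0.4 per patient-year, the same before and after; median survival m of 1, 2, 3 or 5 years, exponential, so death hazard h = ln 2 / m; index dates evenly spread; equally complete recording in both periods; open-ended look-back with records starting on 1.1.2010. That start is the shortest open-ended case, with a mean look-back of 6 years. Censoring for move-out is ignored.

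**Before.** Averaging 1 - exp(-λL) over L from 0 to 12 gives 1 - (1 - exp(-12λ)) / (12λ). For λ = 0.2: 1 - (1 - 0.0907) / 2.4 = 0.621.

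**After.** With k = λ + h, the share with an event before death or the end of study is (λ/k) x [1 - (1 - exp(-12k)) / (12k)]. For λ = 0.2 and m = 1: h = 0.693, k = 0.893, and 0.2239 x (1 - 1/10.72) = 0.203.

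| Rate per year | Before | After, m = 1 / 2 / 3 / 5 years |
|---|---|---|
| 0.1 | 41.8% | 11.3 / 18.2 / 22.7 / 28.1% |
| 0.2 | 62.1% | 20.3 / 31.0 / 37.5 / 44.8% |
| 0.4 | 79.3% | 33.8 / 47.6 / 55.0 / 62.8% |

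A simulation at λ = 0.2 and m = 2 gave 31.0% after and a rate of 0.200 per patient-year.

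**What drives the gap.** Without death the two sides are equal (62.1% each at λ = 0.2), so in this case death alone produces the apparent fall. If records began five years before 2010, the before figure at λ = 0.2 would rise to 86.1%.

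**How much it could hide.** Suppose the rate doubles from 0.2 to 0.4. The before figure is 62.1% and the after figures are 33.8, 47.6 and 55.0% for m = 1, 2 and 3, so a true doubling reads as a decline. At m = 5 the two are about equal (62.8%). For the percentages merely to match at λ = 0.2 before, the after rate must be 6.4, 3.6, 2.7 or 1.9 times as high for m = 1, 2, 3 or 5.

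**When the effect disappears.** Setting 1 - exp(-λL) equal to the after percentage gives the fixed baseline length at which the two agree: 1.0 to 3.3 years across the table. A shorter baseline reverses the direction.

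**Testing the remedies.** Events per patient-year return 0.20 in both periods. Equal 12-month windows with percentages alone do not fully work: at λ = 0.2, 1 - exp(-0.2) = 18.1% before, against (λ/k)(1 - exp(-k)) = 13.2, 15.4 and 16.2% after for m = 1, 2 and 3.

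**The case against.** The strongest reply is that an unlimited look-back is inferred. The parenthesis in the 7.7.4 sentence lists types of data, so the phrase may describe sources and not time. Figure 1 is captioned as showing the study time windows, and it is not visible here. A baseline limit may be there, and its absence from the text cannot be held against the plan. This stands, and it is why the direction is stated only as conditional.

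A reader might infer three stronger things that the documents do not support:
- **That acute events will certainly appear to fall.** Contact with specialty care, and so recording, may be denser after mRCC, which would push the other way. The documents do not settle the net direction.
- **That the artefact is a drop of 37-62 points.** Those values come from fixed look-backs of 6 to 15 years against two years of follow-up for everyone at 0.2 per year (70-95% against 33%). No such look-back lengths are given, and the smallest gap in the table above is about 14 points (41.8% against 28.1%).
- **That a baseline percentage rising with diagnosis year distorts a planned result.** Section 7.2.3 stratifies the secondary objectives by IMDC category only; no morbidity analysis by diagnosis year is planned.

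It is also fair to say that the analysis is descriptive, with no before-and-after test, so no p-value is wrong. Antihypertensives are long-term medication and nephrectomy is essentially a one-off procedure, so the constant-rate model fits neither. None of this makes a yes/no percentage comparable across unmatched periods when one of them is truncated by death.

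**Conclusion.** The point holds in conditional form. For infections and antibiotic use, the before and after percentages in 7.7.4 are not comparable as specified, because each depends on its window length, one window ends at death, and the visible text does not state the other.

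If the look-back is open-ended and recording is equally complete, a constant rate appears as a fall. Across the assumed rates (0.1-0.4 per year) and median survival (1-5 years), the gap is about 14 points (41.8 - 28.1) to 46 points (79.3 - 33.8). The size rests on those assumptions and cannot be derived from the documents. A baseline capped at roughly 1-3 years would remove or reverse the effect.

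The point concerns the before-and-after contrast for acute, recurrent items in a descriptive secondary objective. It does not extend to chronic diagnoses, or to comparisons between IMDC groups after index.

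**What to change.** In 7.7.4:
- Report infections and antibiotic use as events per patient-year in each period, the scaling that 7.7.5 already uses for resource use.
- State the baseline window in the text. The baseline patient-years cannot be formed without its start.
- Treat an equal fixed window before and after index as optional. If it is used, keep the patient-year denominator or allow for death, because percentages alone would still be affected.
- Keep an open-ended look-back only for chronic conditions ever diagnosed and for one-off procedures, and do not contrast those percentages with follow-up.

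The cost is a wording change and a little extra analysis: event counts are needed in place of yes/no flags. Table 2 already lists dates for medications.

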7.9. Limitations of the research methods

All the data is recorded by the hospital during everyday practice and most of the data is stored in structured format. Therefore, rather high quality of the data is expected. However, as with all RWD, it is plausible to have erroneous entries. Also due to the retrospective nature of the study, missing and/or incomplete data is expected in some of the medical records. Patients' records will not be excluded because of missing values, and missing data will not be imputed, i.e. the data will be analyzed as they are recorded in the electronic medical records. The proportion of missing values per variable will be reported.

The treatment lines will be defined based on the medication data and therefore, misclassification of treatment lines is possible. However, the start and end dates of each main drug are expected to be recorded rather precisely, and the clinician PPD will be consulted when constructing the treatment lines. Thus, the majority of the treatment lines are expected to be defined correctly.

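### The before/after morbidity contrast in 7.7.4 mixes true change with differences in recording intensity and window length around mRCC index, so it may rise or fall with no true change

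*Combined protocol and SAP*

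**What the plan says.** Secondary objective 1 (section 6.2) includes "antihypertensive use before and after mRCC diagnosis, as applicable", together with co-diagnoses, procedures, infections and antibiotic use. Table 2 (section 7.3) makes the co-diagnosis variable a "yes/no; co-diagnoses before and after index" indicator. Section 7.7.4 gives the observation periods only as "before and after diagnosis of advanced/metastatic RCC using all available data (ICD-10, procedure codes, and ATC-codes) in baseline and during the follow-up", and reports the number and proportion of patients with each morbidity. The text gives no look-back length, no fixed follow-up length and no rate per unit of time. (Figure 1, on study time windows, was not readable in the copy reviewed.)

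On the source, section 7.3 states: "Source for all variables is the data lake of HDSF". Section 7.9 adds: "All the data is recorded by the hospital during everyday practice". The drug variable is "Medications; including - hospital medications - prescriptions". The documents do not say whether prescriptions issued in primary care are visible.

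On the index, sections 7.2 and 7.2.1 allow an oncologist visit with RCC as main diagnosis, or the start of mRCC treatment, to define it. They state that RCC patients see an oncologist only once the disease has metastasised. Objectives other than primary objective 1 use treated mRCC patients only.

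Section 7.9 covers erroneous entries, missing data and misclassified treatment lines. It does not mention recording that differs before and after index.

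**The concern.** A yes/no indicator of this kind depends on three things: whether the patient has the condition, how often the patient meets the system that records it, and how long the patient is observed. The plan lets the second and third change at index, and then sets the two proportions side by side.

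The two distortions can work against each other. More frequent contact after index pushes the recorded proportion up. A long look-back set against a short follow-up, cut by death or censoring, pushes the after-index proportion down relative to the before-index one. A table of hypertension, antihypertensive use and infections before and after mRCC invites a reading about the disease or its treatment. Neither the size nor the sign of the difference supports such a reading.

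**Working it through.** **The plan's own figure.** The documents state no figure for this analysis. The one planning figure, the mRCC cohort size in section 7.5, reproduces: 1,100 × 0.20 = 220 and 1,100 × 0.50 = 550.

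**Share metastatic at first diagnosis.** Section 5 gives 20–30% metastatic at diagnosis, and relapse in a further 20% of localized patients after nephrectomy. If all localized patients have nephrectomy, the share of mRCC that is metastatic at first diagnosis is p / (p + 0.20(1 − p)):
- p = 0.20: 0.20 / (0.20 + 0.16) = 56%
- p = 0.30: 0.30 / (0.30 + 0.14) = 68%

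If the further 20% is read as 20% of all RCC, the share is 0.20/0.40 = 50% to 0.30/0.50 = 60%. So about half or more would have no earlier RCC follow-up in the source. Patients with local RCC before 2010, whom section 7.2.2 admits, would lower this share.

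**Model with no true change.** All inputs below are assumptions.
- Hypertension: recorded proportion = 0.5 × (1 − exp(−q·c·T)). True prevalence is 50% on both sides. The coding probability per contact q is 0.05 or 0.10, c is contacts per year (before/after pairs 1/12, 2/12 and 2/6), and T is years of window.
- Infections: recorded proportion = 1 − exp(−0.3·k·T). The true rate is 0.3 per person-year on both sides, and k is the fraction captured (before/after pairs 0.2/0.6, 0.2/0.4 and 0.4/0.6).

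Worked case for hypertension, q = 0.05, 2 contacts per year before and 12 after:
- One year each side: before 0.5 × (1 − exp(−0.1)) = 4.8%; after 0.5 × (1 − exp(−0.6)) = 22.6%; ratio 4.74.
- Ten years before, one year after: before 0.5 × (1 − exp(−1.0)) = 31.6%; after 22.6%; ratio 0.71.

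Only the window changed, and the apparent effect reversed. After/before ratios over the full set of inputs:

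| Windows (before v after) | Hypertension | Infections |
|---|---|---|
| 1 v 1 or 2 v 2 years | 2.1 to 9.3 | 1.4 to 2.8 |
| 5 v 2 years | 1.1 to 3.2 | 0.67 to 1.17 |
| 10 v 1 or 2 years | 0.41 to 1.8 | 0.24 to 0.67 |
| Unequal windows, recording intensity unchanged | 0.15 to 0.52 | 0.16 to 0.47 |

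The first row isolates contact or capture, the last isolates window length, and the middle rows combine them. The true ratio is 1 throughout.

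**The case against.** The objective is secondary and descriptive. Section 7.7.4 plans no before/after test or effect estimate, and section 7.8 already includes checks of coverage, change over time and systematic gaps. No contact count or coding probability is documented, so every ratio above rests on assumed inputs. Patients with earlier localized disease may already have had hospital contact for surgery. These points stand, and they limit the severity. They do not answer the concern. Objective 1 names the before/after contrast, the section 7.8 checks are not tied to index, and the fallback for low coverage in 7.7.4 is a drug proxy from the same data lake.

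A reader might infer that recorded hypertension, antihypertensive use and infections are bound to rise at index, several-fold. The documents do not support that. With 3 contacts a year before, 15 after and q = 0.05 per contact, one-year windows give 0.5 × (1 − 0.95^3) = 7.1% against 0.5 × (1 − 0.95^15) = 26.8%, a ratio of 3.8. The plan does not use one-year windows. With five years before and one after, both sides have 15 contacts and the ratio is 1.0. With ten years before, the figures are 39.3% and 26.8%, a ratio of 0.68.

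A reader might also infer that the source holds specialty-care records only. The plan uses specialty care to scope resource use and in the move-out rule ("no contacts to specialty care of HDSF within 2 years"), but it never says so of the morbidity data, and prescriptions are included. How far contact increases at index is likewise not stated.

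**Conclusion.** The concern holds in this form: the N (%) contrast in 7.7.4 cannot be read as a change in morbidity, even if the plan is followed exactly, and the sign of its bias is undetermined. With no true change, the assumed inputs give ratios from 0.41 to 9.3 for hypertension and 0.24 to 2.8 for infections when recording intensity differs across index. The qualitative conclusion needs only what the documents state: a single hospital source, oncology contact that starts at metastasis, ever-recorded indicators, and windows described as all available data. The numerical ranges rest on the assumed contact rates, coding probabilities, capture fractions and window lengths. If Figure 1 fixes equal windows, the window-length part falls away and the contact part remains. This is a worthwhile, inexpensive correction to a secondary objective and does not affect the primary objectives.

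**What to change.** In section 7.7.4:

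1. For each before/after comparison, use the same fixed window on each side of index, for example 12 months. Give patients and events per person-year, as 7.7.5 already does for resource use. This removes the window-length effect and allows for early death or censoring.
2. Equal windows alone leave the contact effect (first row of the table) in place. Report HDSF contacts per person-year in each window beside the morbidity figures, and split results by metastatic at first RCC diagnosis versus later relapse.
3. As a sensitivity analysis only, repeat in patients with at least one contact in each window and report the number dropped, which could be large given the 56–68% above. Show a prespecified negative-control group of chronic codes descriptively. It should not serve as a decision threshold: with zero true change and 3 v 15 contacts, the ratio is (1 − 0.90^15)/(1 − 0.90^3) = 2.9 at q = 0.10 but (1 − 0.98^15)/(1 − 0.98^3) = 4.4 at q = 0.02, so a control coded at a different frequency would mislead.
4. Label results as recorded in the HDSF data lake, state whether primary-care prescriptions are visible, and add differential ascertainment around index to 7.9.

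Do not use codes per 100 contact days as the main measure. If true infections doubled while contacts went from 3 to 15, that index would fall to 2/5 = 0.4 of baseline.

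The cost is plan wording and a few table columns. Contact dates, diagnoses and drug records are already in Table 2. Records outside the fixed windows are not used in the contrast, but can still be described separately.
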